STATISTICAL ANALYSIS. Quantitative variables with normal distribution according to the Kolmogorov-Smirnov test will be expressed as Means \pm Standard Deviation. Quantitative variables with non-normal distribution will be expressed as Medians (Interquartile Range 25-75). Categorical variables will be expressed as proportions (percentages). Change deltas will be calculated for each group and compared using ANCOVA, considering age, sex, BMI, baseline HbA1c, and time since Diabetes diagnosis as covariates. A p-value \leq 0.05 will be considered significant. All analyses will be performed with SPSS 22.0.

Study Timeline

Study Type	Select an option
Retrospective	
Prospective	X

Process of assigning study groups

Maneuver	Yes (Include corresponding information)	No	Not applicable
Randomization	X		
Open-label study	X		
Single-blind study		X	
Double-blind study		X	
Triple-blind study		X	

Description of maneuvers or interventions

- **Clinical History:** Will be conducted via telemedicine (Phone call/Videocall, Whatsapp, Teams, Zoom, Google Forms) at visit 1 DP of the treatment period.
- **Diet Plan Prescription:** Will be conducted via telemedicine (Phone call/Videocall, Whatsapp, Teams, Zoom, Google Forms) at visit 2 DP of the treatment period.
- **Anthropometric Measurements and Physical Exam:** Will be performed at visits 1 DP, 3 DP, 4 DP, and 6 DP of the treatment period.
- **GV Monitoring:** Both groups will be monitored before treatment and at the end. The iPro™ CGM system (Medtronic, Northridge, CA) will be used. Baseline continuous glucose monitoring will begin in week 1 (Visit 1DP) and end seven days later at Visit 2DP (day 1, Week 2). End-of-treatment continuous glucose monitoring will begin at Visit 5 DP (week 12) and end 7 days later (Visit 6 DP).
- **Measurement of HbA1c and Insulin Levels:** Will be performed at visits 1DP and 6DP of

the treatment period.

- **Spot Urine Sample:** Will be collected at Visits 1DP, 3DP, 4DP, and 6DP.
- **Measurement of Oxidative Stress and Inflammation Biomarkers:** Will be performed at visits 1DP, 3DP, 4DP, and 6DP of the treatment period.
- **WHO Physical Activity Questionnaire:** Will be evaluated via telemedicine (Phone call, Whatsapp, Teams, Zoom, Google Forms) at visits 1DP, 3DP, 4DP, and 6DP of the treatment period.

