- **Food Record:** Will be performed at visits 1 FP, 2 FP, 1 DP, 2 DP, 3 DP, 4 DP, 5 DP, and 6 DP of the treatment period. The patient will keep a daily record, and data will be collected via Phone call/Videocall, or e-mail.

Table of Times and Events

Procedure	Visit 1 FP	Visit 2 FP	Visit 1 DP	Visit 2 DP	Visit 3 DP	Visit 4 DP	Visit 5 DP	Visit 6 DP
	Week -2	Week -1	Week 0	Week 1	Week 5	Week 9	Week 12	Week 13
Informed Consent			x					
Weight and Height			x		x	x		x
Pre-randomization Inclusion Criteria*	x							
Clinical History			x					
MET Tolerance Evaluation		x						
Inclusion and	x							

Exclusion Criteria								
Anthropometric Measurements (weight, waist circ., blood pressure)			x		x	x		x
Physical Exam			x		x	x		x
Concomitant Diseases	x							
Concomitant Medications	x							
Glycemic Assessment Monitoring			x				x	
CGM Removal				x				x
WHO Physical Activity Questionnaire	x		x		x	x		x
Food Record (Consumed Diet Assessment)	x		x	x	x	x	x	x
HbA1c Levels			x		x			x
Fructosamine					x	x		
Insulin Levels			x		x	x		x

Oxidative Stress			x		x	x		x
Inflammation Biomarkers			x		x	x		x
Body Fat Quantification			x		x	x		x
Nutritional Counseling and Food Plan				x				

FP: Off-protocol, DP: On-protocol, MCG: Continuous Glucose Monitoring

* Determination of HbA1c levels and BMI

** Lipids (total cholesterol, HDL, LDLc, triglycerides), glucose, ALT, AST, creatinine, creatinine clearance, uric acid, albuminuria)

Treatments (if applicable) (include a table for each study medication)

Medication 1

Item	Include corresponding information	No	Not applicable
Name	Dapagliflozin		
Does it comply with "Good Manufacturing Practices"?	Yes		
Codes, labeling, storage, retention, and safeguarding of drug samples	Yes		
Pharmaceutical form	Tablets of 10 mg		
Dose	1 tablet		

Administration interval	Every 24 hours		
Route of administration	Oral		
Administration speed	Immediate, with a glass of water		
Duration of treatment	12 weeks		

Medication 2

Item	Include corresponding information	No	Not applicable
Name	Metformin		
Does it comply with "Good Manufacturing Practices"?	Yes		
Codes, labeling, storage, retention, and safeguarding of drug samples	Yes		
Pharmaceutical form	Tablet 1000 mg Tablet 500 mg		
Dose	1 tablet of 1000 mg or 2 tablets of 500 mg		
Administration interval	Every 12 hours		
Route of administration	Oral		
Administration speed	Immediate, with a glass of water		
Duration of treatment	12 weeks		

Follow-up

Item	Include corresponding information	No	Not applicable

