Number of study phases	2		
Number of visits and scheduling (include times)	8 Patient visits will be scheduled in the morning, from 8 am to 12 pm, ensuring that appointments during the study occur at the same time for each patient.		
Duration of each study phase	Phase 1, pre-randomization: 2 weeks. Phase 2, treatment: 12 weeks		
Laboratory and imaging studies	HbA1c, insulin, fructosamine, lipid profile, uric acid, serum creatinine, urinary creatinine, serum albumin, urinary microalbumin, inflammation markers, and transaminases.		
Total duration of follow-up	13 weeks		
Sampling methods	Randomisation		
Treatment options offered at the end of the study	Standard glucose lowering medication		

Overdose Management

- **Metformin:** In cases of overdose, gastric lavage and supportive measures according to symptoms will be performed, with close monitoring every 4 hours until clinical resolution.
- **Dapagliflozin:** Due to its mechanism of action, dapagliflozin very rarely causes hypoglycemia even at doses up to 50 times that used in this study. However, in case of

overdose, appropriate supportive treatment will be provided as indicated by the patient's clinical status, with close monitoring every 4 hours until clinical resolution.

Rescue Therapy

According to the ADA/EASD 2019 guidelines [49], at 12 weeks, it will be assessed whether the patient reaches HbA1c targets. If the individualized target is not met, or if the patient has fasting glucose > 140 mg/dL at any visit, rescue therapy will be administered:

- **Group 1:** Dapagliflozin 10 mg/day + Metformin 2000 mg/day + glimepiride or glibenclamide or gliclazide or glipizide.
- **Group 2:** Metformin 2000 mg/day + glimepiride or glibenclamide or gliclazide or glipizide.

If the patient has postprandial glucose > 180 mg/dL on capillary blood glucose monitoring at home, rescue therapy will be added:

- **Group 1:** Dapagliflozin 10 mg/day + Metformin 2000 mg/day + glimepiride or glibenclamide or gliclazide or glipizide.
- **Group 2:** Metformin 2000 mg/day + glimepiride or glibenclamide or gliclazide or glipizide.

Permitted Concomitant Therapies

Medications for concomitant medical conditions will be permitted. However, caution should be taken when using the following drug groups, given their interaction with Metformin:

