- Diagnosis of T2D: if a patient has taken any drug and/or insulin, they will be prescribed only Metformin as a washout period in the pre-randomization phase for 2 weeks.

b) Exclusion criteria

- Complications related to T2D and catabolic symptoms.
- HbA1c $>$ 9% with catabolic symptoms.

- CKD-EPI creatinine clearance: <60 ml/min.
- LADA or T1D.
- Concomitant clinically significant disease such as: liver, hematological, oncological, psychiatric, or rheumatic disease.
- Symptoms of markedly uncontrolled diabetes: (marked polyuria or polydipsia + 10% weight loss within the last 3 months before enrollment).
- Known hypersensitivity to dapagliflozin, metformin, or any of the drug excipients.
- Unstable or rapidly progressing kidney disease.
- Patients with severe liver failure (Child-Pugh class C).
- Patients with bariatric surgery.
- Any major CV event / vascular disease within 3 months before signing consent at enrollment, as assessed by the investigator.
- For women only: currently pregnant (confirmed with a positive pregnancy test) or lactating.
- Being hospitalized or having less than one month since hospital discharge.

c) Elimination criteria

- Allergy to dapagliflozin, severe life-threatening illness, or pregnancy during the study.
- Patients presenting with acute renal failure (decrease in > 40% of GFR)
- For women only: pregnancy confirmed with serum chorionic gonadotropin. In case of pregnancy during the study, the subject must be eliminated from the trial, offered standard treatment indicated in point 36, and the Pregnancy Outcome Report (Annex) must be completed to record essential details of the mother. Part I should be completed after pregnancy identification and Part II is to record the pregnancy outcome.

39. Outcomes and Variables

- **Primary Variable:** Change from baseline in GV (MAGE) in mg/dL after 12 weeks of treatment between the DAPA+ MET group versus the MET monotherapy group.
- **Secondary Variables:**
 - Change from baseline (absolute difference) in HbA1c levels (%) after 12 weeks of treatment between the DAPA + MET group versus the MET monotherapy group.
 - Change from baseline (total difference) in insulin levels (μ U/mL) after 12 weeks of treatment between the DAPA + MET group versus the MET monotherapy group.
 - Change from baseline (absolute difference) in oxidative stress measurement (total antioxidant capacity) after 12 weeks of treatment between the DAPA + MET group versus the MET monotherapy group.

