## Statistical Analysis Plan

The sample size was determined using the mean difference formula:  $n = (Z\alpha / 2 + Z\beta) 2 * 2 * \sigma^2 / d^2$  a reduction in GV was estimated from 4.85 to 2.2 with an expected standard deviation of 2.8 in the MAGE index according to RR. Henry et al. [19] with an alpha value of 0.05 and a power of 0.80, resulting in a sample size of 88 subjects, with 44 subjects in each treatment group.

Patient recruitment began in October 2019 and was interrupted due to the SARS-COV-2 pandemic in March 2020. Nevertheless, patients who were already enrolled were followed up. Recruitment was normally restarted in March 2021; one of the inclusion criteria was adjusted, allowing HbA1c <13.0%, prior limit <12.0%. The last patient was recruited on December 6th, 2021. The complete study was concluded in March 2021.

A total of 88 patients met the selection criteria, signed the informed consent, and were randomized 1:1 on [www.randomization.com](http://www.randomization.com) (complete list of it is showed as supplementary material) to receive daily either DAPA 10 mg + MET 2000mg or MET 2000mg for 12 weeks. Both groups were monitored for GV using a CGM system for 7 days at baseline (W0) and on week 12 (W12).

Pre-randomization: patients were given 2000mg of MET daily for two weeks, only patients who tolerated this dose were included in the study and a treatment was randomly assigned.

Treatment: subjects who met the pre-randomization period and tolerated treatment were randomized 1:1 to receive either DAPA 10 mg/day + MET 2000 mg/day or MET 2000 mg/day for 12 weeks.

Of the total of 264 patients surveyed, a sample of 88 met the inclusion criteria and none of the exclusion criteria randomization DAPA+MET n=42 and MET n= 46. During the study, 7 patients discontinued (DAPA+MET n=1 and MET n=6). 80 patients concluded the study for 12 weeks (DAPA+MET n=41 and MET n=39). One patient was removed from the study (MET n=1) because he did not comply his medication intake nor the instructions during CGM. Study flowchart is displayed in Figure 1.

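### The only scheduled informed consent (Week 0) falls after the two-week pre-randomisation phase in which prior treatment is replaced by metformin and tolerance is tested

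*Protocol*

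**What the plan says.** The Table of Times and Events in the protocol has eight visit columns. Its legend reads "FP: Off-protocol, DP: On-protocol", which makes Visit 1 FP (Week -2) and Visit 2 FP (Week -1) off-protocol and starts the protocol proper at Visit 1 DP (Week 0). The Informed Consent row carries a single mark, at Visit 1 DP. The row "MET Tolerance Evaluation" also carries a single mark, at Visit 2 FP.

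Other parts of the documents describe what happens in the weeks before that consent:

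- The Follow-up table divides the study as "Phase 1, pre-randomization: 2 weeks. Phase 2, treatment: 12 weeks".
- Selection Criteria, under inclusion, says that "if a patient has taken any drug and/or insulin, they will be prescribed only Metformin as a washout period in the pre-randomization phase", for two weeks.
- The pre-randomisation paragraph of the SAP reports that "patients were given 2000mg of MET daily for two weeks, only patients who tolerated this dose were included in the study".
- The text on the food record says it "Will be performed at visits 1 FP, 2 FP, 1 DP" and at the later visits, so study data are collected at the FP visits too.

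The only other dating of consent is in the exclusion criteria, where the look-back for a cardiovascular event runs "within 3 months before signing consent at enrollment". No week is given for enrolment.

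**The concern.** A washout is done for the trial. For an untreated patient, starting metformin may look like usual care. Stopping insulin or another glucose-lowering drug in order to qualify does not, least of all in a population whose HbA1c may be anywhere below 12% (below 13% after the change reported in the SAP). Consent should come before that step.

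On the printed schedule, a patient could have treatment withdrawn, take run-in metformin, fail the tolerance check, and leave without ever reaching the visit at which consent is sought. What is at stake is participant protection and a clear consent date. The comparison of the two arms is not affected, because everything described here happens before randomisation.

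**Working it through.** No sample size, power or alpha figure is involved. The check is a timeline, followed by a count of the extra consents.

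**1. Is the column reading sound?** The table was read from a PDF, so the position of the consent mark needs an anchor. Clinical History has one mark in the same column as Informed Consent, and the description of maneuvers places it "at visit 1 DP of the treatment period". Anthropometry and Physical Exam are marked in the third, fifth, sixth and eighth columns, that is 1, 3, 4 and 6 DP, which is what the text says. The columns are aligned, and the consent mark is at Week 0.

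**2. Timeline as printed.**

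| Week | Visit | Scheduled |
|---|---|---|
| -2 | 1 FP | HbA1c and BMI determination, eligibility checks, concomitant diseases and medications, activity questionnaire, food record |
| -2 to 0 | pre-randomisation phase | metformin-only washout of prior treatment (protocol); metformin 2000 mg/day run-in (SAP) |
| -1 | 2 FP | metformin tolerance evaluation |
| 0 | 1 DP | **informed consent**, clinical history, physical exam, start of baseline CGM |

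Consent minus first visit: 0 - (-2) = 2 weeks. Consent minus tolerance evaluation: 0 - (-1) = 1 week.

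**3. Is the earlier period trial activity or routine care?** The off-protocol label suggests routine care, but the rest of the protocol does not:

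- The Follow-up table makes these two weeks the first of two study phases.
- The protocol counts 8 visits, under Follow-up and again under costs. The table reaches 8 only if both FP visits are included (2 FP + 6 DP = 8), and the study group pays for transport.
- The section on recruitment potential treats those who enter the pre-randomisation period as having started the project.
- The washout is written into the trial's own inclusion criteria, and the SAP makes tolerating the run-in a condition of inclusion.

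The drug change and run-in dosing are therefore directed by the trial.

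**4. How many extra consents would earlier consent mean?** The plan expects about 15% of entrants not to reach treatment and about 102 to be assessed.

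- The plan's figure is consistent with 88 × 1.15 = 101.2, rounded up to 102. Then 102 - 88 = 14, and 14/102 = 13.7%.
- Applying the 15% loss to entrants, as it is worded: 88/0.85 = 103.5, rounded up to 104. Then 104 - 88 = 16, and 16/104 = 15.4%.

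These are planning figures only. The SAP reports 264 surveyed and 88 randomised, so 264 - 88 = 176 were not randomised. How many of those entered the run-in is not stated, nor how many were on a prior drug or insulin.

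**The case against.** The strongest objection is that the point rests on one mark in a table with other faults. HbA1c is marked at Visit 3 DP and insulin at Visits 3 and 4 DP, while the text gives both only at 1 and 6 DP. The activity questionnaire is marked at Visit 1 FP, but the text lists DP visits only. The food record is at Visit 2 FP in the text and unmarked there in the table. A double-asterisk laboratory footnote has no row. The exclusion criterion dated from consent, with eligibility marked at Week -2, also fits an intention to take consent at Week -2. The consent pages were removed before review, so a screening consent cannot be ruled out.

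Most of this stands. It makes a clerical slip plausible, and it limits what can be said about conduct. It does not rescue the printed schedule: no earlier consent is scheduled, and a misplaced mark needs the same correction.

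Three further inferences are tempting, and the documents do not support them:

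- **The SAP confirms late consent.** It lists criteria met, consent signed, randomised, but does not say where the run-in falls in that sequence. The sentence fits consent before the run-in equally well.
- **With consent at Week 0, nothing covers the last two weeks of the cardiovascular look-back.** Clinical history and physical exam are both scheduled at that visit. Only the formal eligibility row lacks a mark.
- **The planning loss caps the number treated without consent.** It does not, given the 176 surveyed patients who were not randomised and the unreported run-in entry.

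A last objection is that recruitment is finished, so moving a mark changes nothing for these patients. That is true of the mark. The statement of consent dates can still be made.

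**Conclusion.** The point holds as a fault in the schedule. As printed, trial-directed drug withdrawal and run-in dosing begin up to two weeks before the only scheduled consent, and the tolerance evaluation comes one week before it. This rests on the column alignment, which the text confirms, and on reading the washout and run-in as trial procedures, which the phase structure, visit count and inclusion criteria support.

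A reader might infer that patients did have treatment stopped before they had consented. The documents do not show that. They contain no consent dates, and an earlier or separate consent may have existed. Confidence is therefore medium: firm on the schedule, open on conduct. No bias in the comparison between arms follows.

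**What to change.** 1. In the Table of Times and Events, move the Informed Consent mark from Visit 1 DP to Visit 1 FP (Week -2), before any drug is stopped or run-in metformin is given. If a separate screening consent was used, add it to the table at that visit instead.
2. Relabel the FP visits as on-protocol.
3. In the SAP or the study report, state when consent was signed relative to the first run-in dose or the withdrawal of prior treatment. Notify the ethics committee of anyone treated before consent. Treatment given according to the printed schedule would be a consent matter for that committee, not a departure from the protocol.

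The first two changes are one mark and one label. With recruitment over, they correct the record and any reuse of the schedule. The third is what can still be acted on for this trial, and it needs only the signed consent dates. The operating cost of earlier consent is asking patients who are never randomised, about 14 to 16 on the planning figures; the actual number is unknown.

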The baseline characteristics were, the age [53.7  $\pm$  8.6 years DAPA+MET versus 50.9  $\pm$  11.8 years MET; p=0.2], TIR% Target: 70-180 mg/dL [55.5% (12.6-80.6) DAPA+MET versus 82.7% (26.1-95.1) MET; p=0.02], BMI [30.9  $\pm$  6.9 kg/m^2 DAPA+MET versus 30.1  $\pm$  3.2 MET; p=0.24], glucose [202.4  $\pm$  70.5 mg/dL DAPA+MET] versus 179.0  $\pm$  62.9 mg/dL MET; p=0.11], insulin [12.2  $\pm$  13.3  $\mu$ U/mL DAPA+MET versus 10.9  $\pm$  6.6  $\mu$ U/mL MET; p=0.57]. Complete baseline characteristics of the subjects included are summarized in Table 1.

All the measurements were carried out fasting. Student's T test was performed for normal variables to obtain significance. Skewed distribution variables are expressed with median and interquartile values of 25% and 75%, significance for these variables was obtained with the Mann Whitney U test.

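### The fasting-glucose rescue trigger excludes no visit, yet most patients probably exceed it at entry, and no analysis rule covers MAGE recorded after rescue has started

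*Protocol*

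**What the plan says.** **Rescue rule (Protocol, Rescue Therapy).** One trigger is an HbA1c check: "at 12 weeks, it will be assessed whether the patient reaches HbA1c targets". A second is that "if the patient has fasting glucose > 140 mg/dL at any visit, rescue therapy will be administered". A third, based on postprandial capillary readings at home, has no time window. Rescue is an add-on to the assigned regimen, in Group 1 "Dapagliflozin 10 mg/day + Metformin 2000 mg/day + glimepiride or glibenclamide or gliclazide or glipizide" and in Group 2 metformin with the same choice of fourth-listed agents.

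**CGM timing (Protocol, Description of maneuvers or interventions).** The baseline recording runs from Visit 1 DP to Visit 2 DP and is described as taking place before treatment. For the final one, "End-of-treatment continuous glucose monitoring will begin at Visit 5 DP (week 12) and end 7 days later (Visit 6 DP").

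**HbA1c timing.** The same section says of HbA1c and insulin: "Will be performed at visits 1DP and 6DP of" the treatment period. The Table of Times and Events adds an HbA1c draw at 3 DP. Neither lists one at 5 DP.

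**Baseline glucose (SAP).** Glucose was 202.4 (SD 70.5) mg/dL in DAPA+MET and 179.0 (SD 62.9) mg/dL in MET, p=0.11. The SAP adds: "All the measurements were carried out fasting". Randomised numbers were "DAPA+MET n=42 and MET n= 46".

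**Analysis.** The protocol's Statistical Analysis section names one reason for leaving patients out, an acute stress event. Neither it nor the SAP says what happens to MAGE in patients who received rescue, and the SAP gives no rescue count.

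**The concern.** A rescue rule normally separates patients who fail on assigned treatment from the rest. If the trigger sits below the entry mean of both arms and applies at every visit, it cannot do that. Taken literally, it adds a third drug to most participants at Visit 1 DP, when the baseline CGM sensor is placed. The baseline MAGE would then no longer be a pre-treatment value.

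The second exposure is at the other end of the trial. Rescue begun at any visit before the final recording may still be acting while the primary endpoint is measured. Rescue depends on glucose, the trial is open-label, and the arms are expected to differ in glucose, so rescue use may differ by arm. The change in MAGE would then mix the randomised contrast with rescue, and the plan does not say which effect it intends to estimate.

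The HbA1c limb raises a smaller matter: the visit at which a decision at 12 weeks is to be made cannot be identified from the schedule.

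**Working it through.** **1. Reproduce the plan's own figure.** With n = 42 and 46, the standard error of the difference is √(70.5²/42 + 62.9²/46) = √(118.3 + 86.0) = 14.3. Then t = (202.4 − 179.0)/14.3 = 1.64 and Welch p = 0.105, which rounds to the stated 0.11. The means and SDs are therefore consistent with the randomised arm sizes.

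**2. Share above 140 mg/dL at baseline.** Normal shape: P = Φ((mean − 140)/SD).

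- DAPA+MET: (202.4 − 140)/70.5 = 0.885, P = 0.812.
- MET: (179.0 − 140)/62.9 = 0.620, P = 0.732.
- Pooled: (42 × 0.812 + 46 × 0.732)/88 = 0.770.

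Other shapes with the same mean and SD:

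| Shape | DAPA+MET | MET | Pooled |
|---|---|---|---|
| Normal | 81% | 73% | 77% |
| Log-normal | 82% | 71% | 76% |
| Gamma | 81% | 71% | 76% |
| Distribution-free floor | 44% | 28% | 35% |

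The floor is the one-sided Chebyshev (Cantelli) bound, (mean − 140)²/(SD² + (mean − 140)²):

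- DAPA+MET: 3893.8/8864.0 = 0.439.
- MET: 1521.0/5477.4 = 0.278.

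The three ordinary shapes put about 67 to 68 of 88 patients above the trigger. The floor shows that mean and SD alone do not prove a majority.

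**3. Where the literal trigger falls.** Visit 1 DP is when the baseline CGM starts, and the recording ends at 2 DP. A rescue start at 1 DP therefore lies inside a recording described as pre-treatment.

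**4. Which visit is meant by 12 weeks.**

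- Counting from 1 DP (Week 0 in the table): 0 + 12 = Week 12 = 5 DP. The final CGM starts there and no HbA1c is drawn.
- Counting treatment from 2 DP (Week 1), because the baseline CGM precedes treatment: 1 + 12 = Week 13 = 6 DP. HbA1c is drawn there and the CGM is removed.

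The numbering itself differs. The GV Monitoring text puts 1 DP in week 1 and 2 DP on day 1 of week 2, while the table has Week 0 and Week 1.

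**5. Effect on MAGE.** The documents give no follow-up glucose and no rescue counts, so neither the size nor the direction of any effect on the primary contrast can be calculated.

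**The case against.** The strongest reply is that the rule was never meant for entry. Rescue is written as an addition to each randomised regimen, and the Description of treatment groups offers it if necessary within those groups, so an on-treatment reading is natural. That has force, but no passage states the limit, and the words used are unrestricted.

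A reader might go further and infer that most patients were in fact started on a sulfonylurea at entry. The documents do not support that, since the SAP reports no such event.

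A reader might also infer that the HbA1c check collides with the final CGM. That holds only if 12 weeks means the table's Week 12. The other count ends at 6 DP, and it fits the 12-week treatment phase, the 13-week total follow-up and the HbA1c endpoint, whose only end-of-treatment draw is at 6 DP. On that count the decision follows the recording. What remains is ambiguous timing, not a demonstrated collision.

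It is likewise tempting to say that the MET arm would be rescued more often and the contrast reversed. At entry the estimates point the other way (81% DAPA+MET against 71-73% MET), and nothing is reported after entry.

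Three limits on the estimate also stand. The shares are modelled, not counted. They assume that the SAP's baseline glucose is the Visit 1 DP value. The SAP population was partly enrolled under a widened HbA1c limit (<13.0% instead of <12.0%). In addition, the schedule row for the laboratory footnote that lists glucose is not visible in the available text, so the later visits with fasting glucose cannot be listed.

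**Conclusion.** The point holds as a conflict between a written rule and the trial's own figures, together with a gap in the analysis plan. Both baseline means exceed the 140 mg/dL trigger, by 62.4 and 39.0 mg/dL. An estimated 81-82% of DAPA+MET and 71-73% of MET patients would meet it at entry, given an ordinary distribution shape. Applied as written, the rule would place rescue inside the baseline recording for most patients.

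Independently of how the entry question is settled, rescue begun at any visit before the final CGM can be active during the primary measurement, and no rule covers it. Whether this diluted, inflated or left unchanged the MAGE contrast is unknown.

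The HbA1c timing is a matter of inconsistent week numbering and an unnamed decision visit.

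**What to change.** **Reconcile the text.** Rescue Therapy, the GV Monitoring and HbA1c paragraphs, the Table of Times and Events and the SAP baseline figures must be made to agree on which visits the fasting trigger covers and which visit is meant by 12 weeks, with one week numbering throughout. No position is taken here on the threshold, the rescue drug or when rescue should be given.

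**Report rescue.** Retrieve the start date and trigger of every rescue, including starts prompted by home readings, and tabulate rescue use by arm and by timing relative to both CGM windows.

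**Analyse it.** Keep the primary MAGE comparison in all randomised patients, in their assigned arms and regardless of rescue. Add a sensitivity analysis for CGM data recorded after any rescue start. Restricting it to starts at 5 DP or later would miss starts from 1 DP to 4 DP. Excluding post-rescue data is a post-randomisation selection that may differ by arm, and a patient rescued before the final sensor is placed would have no final MAGE left. Such an exclusion therefore belongs only in the sensitivity analysis, with that caveat stated.

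**Cost.** The SAP describes completed follow-up, so an amendment can no longer change conduct. What remains workable is date retrieval from source records, one table and one additional analysis. No visits or assays are needed.
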